Barre Exercise in Parkinson's
NCT Number: NCT06203990

5/20/2025

I. SPECIFIC AIMS

The primary objectives of this study are to: 1) evaluate the feasibility and acceptability of a barre exercise intervention and 2) gather preliminary data regarding the effect of a barre exercise intervention on balance, strength, functional mobility and quality of life in individuals with mild to moderate Parkinson disease (PD). Individuals with PD (N=15) will be recruited to participate in a pilot barre exercise class led by a certified barre instructor. The intervention will include 24, 45-50 minute group classes (twice weekly for 12 weeks, excluding holidays). Pre- and post-intervention data collection will include assessments of balance, lower extremity strength, and functional mobility.

Specific Aim 1: Assess the feasibility and acceptability of a pilot barre exercise intervention for individuals with mild to moderate PD.

Hypothesis 1a: Participants will participate in the intervention, defined as 75% of participants attending and engaging in 75% of the exercise sessions.

Hypothesis 1b: Participants will complete the intervention study, defined as 75% of total recruited participants remaining enrolled for the total duration of the study.

Hypothesis 1c Participants will rate the intervention as acceptable and satisfactory, as measured by a post-intervention survey.

Specific Aim 2: Determine preliminary effects of a pilot barre exercise intervention on balance, strength, functional mobility and quality of life in individuals with mild to moderate PD.

Hypothesis 2a: Barre will improve functional balance, defined as an improved score on the Mini-BESTest.

Hypothesis 2b: Barre will improve functional lower extremity strength, defined as decreased time taken to complete the Five Times Sit to Stand assessment.

Additional functional strength assessments explored include a timed stair ascent and descent task and the Timed Up and Go test.

Hypothesis 2c: Barre will improve functional mobility, defined as an improvement in average gait speed measured in the Ten Meter Walk Test. Additional gait assessments explored include fast as possible and backwards walking in the Ten Meter Walk Test and distance covered in the Two Minute Walk Test.

Exploratory Hypothesis 2d: Barre will improve quality of life, as measured by the Parkinson's Disease Questionnaire (PDQ-39).

II. BACKGROUND AND SIGNIFICANCE

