If the participant meets the inclusion criteria following in-person screening, sensors will be placed on both feet, wrists, the sternum, and lumbar spine to record data during gait, balance, and functional strength assessments. All participants will be also be fitted with a gait belt and closely monitored by members of the research team to prevent falls.

Balance Assessment: Participants will first complete the Mini-BESTest, which is a clinically relevant balance test that is both valid and reliable for individuals with PD.²⁶ The sensors will record postural sway and gait data during the various sections of this test.

Gait Assessments: After completing the Mini-BESTest, participants will complete gait assessments. The sensors will record spatiotemporal gait variables during each walking task.

Two Minute Walk Test: This gait assessment will be used to measure walking endurance. Participants are asked to cover as much ground as possible over the course of two minutes. Following this assessment, the Borg Scale Rating of Perceived Exertion will be administered to measure exertion levels during the Two Minute Walk Test.

Ten Meter Walk Test: This gait assessment will be used to assess average gait speed. Participants will be asked to complete this test under three conditions: 1) normal forwards gait speed, 2) fast as possible gait speed, and 3) backwards walking at a normal, safe gait speed. Only the first condition, normal forwards gait speed, will be used as a primary outcome.

Functional Strength Assessments: Following the gait assessments, participants will complete the following functional strength assessments. These assessments will serve as proxy measures for lower extremity strength. The Borg Scale Rating of Perceived Exertion will again be administered following all of the functional strength assessments listed below.

Five Times Sit to Stand: Participants will be asked to start sitting with their arms folded across their chest and with their back against the chair. Participants are then asked to stand up and sit down five times as quickly as they can.

Stair Ascent and Descent: Participants will be asked to ascend and descend one flight of stairs (building's standard flight of 12 stairs) as quickly and safely as possible under close supervision by a research team member.

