All assessments and procedures will be repeated after completion of the barre exercise program as mentioned in “Pre-Intervention Visit 1”. This includes the MDS-UPDRS-III, the New Freezing of Gait Questionnaire (NFOG-Q), all motor assessments, and the PDQ-39.

Again, all motor assessments, including the MDS-UPDRS-III, balance, gait, and functional strength assessments will be filmed with participant consent. Video records will again be destroyed after all analyses and publications are complete.

An additional survey will be administered, measuring participant experiences with the exercise classes, including satisfaction and acceptability.

OUTCOME MEASURES

A variety of outcome measures will be used for this study.

- Primary Outcomes
 - Feasibility and Acceptability

- Participation- defined as the number of individuals who attend and participate in at least 75% of the classes
 - Retention- defined as the percentage of participants who complete the intervention, regardless of the number of sessions they attended
 - Client Satisfaction and Acceptability Questionnaire (CSQ)- mean group rating on measure of self-reported satisfaction of a program
- Secondary Outcomes
 - Balance
 - Mini-BESTest— a measure that quantifies overall balance dysfunction
 - Gait
 - Gait Speed in the 10MWT- a measure of how quickly someone walks at their normal, comfortable gait speed across a 10-meter distance; measured in meters/second
 - Functional Strength
 - Five Times Sit to Stand Time – total time it takes for an individual to perform five repetitions of standing up and sitting back down in a chair as quickly as possible
- Additional Outcomes
 - Gait
 - 10MWT fast as possible gait speed- a measure used to assess average maximum gait speed to determine ability to modulate gait
 - 10MWT backwards walking at comfortable pace – a measure used to assess gait speed in a more challenging condition that also assesses dynamic balance and spatial awareness
 - 2MWT distance- total distance a person can cover while walking continuously for two minutes; a measure of walking endurance
 - Functional Strength
 - Stair Ascent and Descent – total time it takes for an individual to ascend and descend a standard flight of 10 stairs as quickly and safely as possible
 - TUG- total time it takes for an individual to stand up from the chair, walk three meters, and sit back down in the chair at normal, comfortable gait speed
 - Quality of Life

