 - Parkinson Disease Questionnaire (PDQ-39) – a patient-reported questionnaire that assesses PD-specific health quality of life in the past month
 - New Freezing of Gait Questionnaire (NFOG-Q) – a patient-reported questionnaire that assesses frequency, severity, and duration of freezing of gait episodes
 - Borg Rating Scale of Perceived Exertion – a 15-point scale with written descriptors designed to standardize perceived exertion across tasks and individuals

The following forms and assessments will also be collected during Pre-Intervention Visit 1:

- Montreal Cognitive Assessment (MoCA)- a valid, sensitive screening tool for mild cognitive impairment
- Demographics Form
- Medical History
- Medication List
- Current exercise habits survey
- Activities-specific Balance Confidence Scale (ABC) – a patient-reported questionnaire that assesses balance confidence while performing various activities
- MDS-UPDRS- gold standard measure of global disease severity in PD, including motor and non-motor symptoms as well as activities of daily living

IV. STATISICAL ANALYSES

Aim 1: Assess the feasibility and acceptability of a pilot barre exercise intervention for individuals with mild to moderate PD.

- Feasibility Objectives
 - Participation: 75% of participants will attend 75% of the 24 sessions.
 - Retention: 75% of recruited participants will complete the intervention and remain enrolled for the duration of the study.
- Satisfaction and Acceptability- Demonstrate that this group exercise class is acceptable, defined as a minimum average rating of > 1.5 out of 4 on the Client Satisfaction and Acceptability Questionnaire (CSQ).

Due to the preliminary nature of the study and small expected sample size, only motor trends, defined as average group change in score from pre- to post-intervention will be reported. Additionally, published MCIDs will be used to establish if the average improvement of the group reached clinical significance.

Aim 2: Determine the effects of a pilot barre exercise intervention on balance, strength, functional mobility and quality of life in individuals with mild to moderate PD.

Hypothesis 2a: Barre will improve functional balance, defined as an improved score on the Mini-BESTest.

- MCID- A 4-point increase in total score will denote a clinically-meaningful improvement in functional balance.²⁷

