Hypothesis 2b: Barre will improve functional lower extremity strength, defined as decreased time taken to complete the Five Times Sit to Stand assessment.

Additional functional strength assessments explored include a timed stair ascent and descent task and the Timed Up and Go test.

- MCID- A 2.3 second decrease²⁸ will denote a clinically-meaningful improvement in Five Times Sit to Stand assessment. There are no valid MCIDs for the timed stair ascent and descent task and the Timed Up and Go test. Therefore, a small effect size will be considered a positive effect for each of these tests.

Hypothesis 2c: Barre will improve functional mobility, defined as an improvement average gait speed measured in the Ten Meter Walk Test. Additional gait assessments explored include fast as possible and backwards walking in the Ten Meter Walk Test and distance covered in the Two Minute Walk Test.

- MCID- A 0.05 m/s increase in gait speed will denote a moderate clinically-meaningful improvement in forward, normal gait speed.²⁹ There is no valid MCID for the Two Minute Walk Test. Therefore, a small effect size will be considered a positive effect.

Exploratory Hypothesis 2d: Barre will improve quality of life, as measured by the Parkinson's Disease Questionnaire (PDQ-39).

- MCID- A 4.22-point increase on the PDQ-39 will denote clinically-meaningful improvement in quality of life.³⁰

V. MONITORING

The data safety and monitoring plan includes recording all reportable events according to the IRB policy. The PI will review all reportable events as they occur.

Study progress and safety will be checked monthly for accuracy, compliance, and completeness by the senior scientist and concerns will be discussed with the PI.

References

2. Jankovic J. Parkinson's disease: clinical features and diagnosis. *J Neurol Neurosurg Psychiatry.* 2008;79(4):368-376. doi:10.1136/jnnp.2007.131045

4. K S. Levodopa unresponsive symptoms in Parkinson disease. *Mov Disord Off J Mov Disord Soc.* 2008;23 Suppl 3. doi:10.1002/mds.22049

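### Does it matter that normal gait speed is labelled both primary and secondary, and that the stair test has 12 stairs in one place and 10 in another?

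*Combined protocol and SAP*

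**What the plan says.** Section III, Pre-Intervention Visit 1, describes three Ten Meter Walk Test conditions (normal forward, fast, backward) and adds: "Only the first condition, normal forwards gait speed, will be used as a primary outcome".

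The Outcome Measures part of section III has three tiers. The primary tier holds participation, retention and the satisfaction questionnaire (CSQ). The secondary tier holds the Mini-BESTest, the Five Times Sit to Stand and "Gait Speed in the 10MWT- a measure of how quickly someone walks at their normal, comfortable gait speed across a 10-meter distance". The additional tier holds, among others, fast and backward walking, the stair test and the PDQ-39.

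Section I opens with: "The primary objectives of this study are to: 1) evaluate the feasibility and acceptability of a barre exercise intervention and 2) gather preliminary data".

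For the analysis, section IV states that "only motor trends, defined as average group change in score from pre- to post-intervention will be reported", and under Hypothesis 2c that "A 0.05 m/s increase in gait speed will denote a moderate clinically-meaningful improvement in forward, normal gait speed".

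On the stair test, the visit description uses the building's "standard flight of 12 stairs", whereas Outcome Measures defines the result as "total time it takes for an individual to ascend and descend a standard flight of 10 stairs as quickly and safely as possible". Section IV, Hypothesis 2b, finds no valid MCID for this test or the Timed Up and Go and says: "Therefore, a small effect size will be considered a positive effect for each of these tests".

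**The concern.** One measure carries two labels in one current document. A plan should fix its primary outcomes before the data are seen. If it does not, a favourable gait result could be presented as primary and an unfavourable one as secondary, with the protocol cited for either choice. That would be unwelcome in a study of 15 people with no control group. Section I seems to add doubt, because it counts gathering preliminary effect data among the primary objectives, and Hypothesis 2c defines functional mobility by gait speed.

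The stair test raises a different worry. The two sections cannot both describe the same flight. Times recorded on 12 stairs but published under a 10-stair definition would misinform readers about the task and spoil any comparison of raw times with other data.

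**Working it through.** The documents give no alpha, power, standard deviation or sample-size formula, so there is no stated figure to reproduce. The check sets the sections side by side and asks what depends on each mismatch.

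**Label of normal gait speed**

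1. Count of primary outcomes. By the Outcome Measures list: participation, retention, CSQ = 3. If the visit description is taken at its word: 3 + 1 = 4.
2. Which reading fits the rest of the document. The Mini-BESTest and the Five Times Sit to Stand have the same standing under Aim 2, and neither is called a primary outcome anywhere. The outcome list puts gait speed beside them. The sentence in the visit description serves to separate one walking condition from the other two, and the list does the same by moving the fast and backward conditions to the additional tier. The list is the only place that sets out a hierarchy, so the word in the visit description is most likely a slip or a loose use meaning the main condition.
3. Section I. A primary objective of gathering preliminary effect data can be served by secondary outcomes. An objective is not an outcome, so section I does not contradict the list.
4. What depends on the label:

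| Item | If primary | If secondary |
|---|---|---|
| Quantity reported (section IV) | mean change | mean change |
| Benchmark (Hypothesis 2c) | 0.05 m/s | 0.05 m/s |
| Hypothesis test or alpha | none planned | none planned |
| Sample size | 15, no power calculation | 15, no power calculation |
| Feasibility targets (75% participation, 75% retention, CSQ above 1.5 of 4) | gait speed not used | gait speed not used |

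Every row is the same in both columns.

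**Stair count**

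1. Procedure 12, outcome definition 10; difference 12 − 10 = 2 stairs.
2. The recorded quantity is the time on the flight actually climbed. Neither the mean change nor a standardised effect size uses the number of stairs, so neither value depends on which count is printed.
3. Post-Intervention Visit Two repeats the assessments of Visit 1. If the flight is the same at both visits, each participant's change compares like with like.
4. The criterion is a small effect size. No threshold in seconds exists that a different flight could shift.

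**The case for a change.** The strongest case for acting is that both contradictions are plain on the page, correction is nearly free, and an outcome hierarchy should not have to be inferred. The visit description uses the very term that the outcome list uses as a formal heading, and section IV attaches no label that would break the tie. For the stairs, no reading reconciles 12 with 10.

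Part of this stands. The wording is inconsistent, and a report that gave stair times under the wrong count would misdescribe the task. The rest carries less weight. A dedicated three-tier list outranks an aside in a test description, so the room for choosing a label after seeing the data is small. Even if the label were misused, the published number and its benchmark would be unchanged, and the result would still be an uncontrolled mean change. There is no error rate to inflate. A reading of section I that made every Aim 2 measure primary goes too far: it would take in the PDQ-39, whose hypothesis that same section calls exploratory. The stair test sits in the lowest tier, and whoever runs it knows which flight was climbed.

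**Conclusion.** The two mismatches are genuine but clerical. The first is one word on the status of gait speed (3 primary outcomes against 4); the second is a count differing by 2 stairs. Neither alters an estimate, a benchmark, a feasibility target or a conclusion. An analyst would follow the Outcome Measures list for the label and describe the flight actually used, and would obtain the same results as under any reconciled wording.

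This rests on three assumptions: the motor outcomes stay descriptive, as section IV states; the same flight is used at both visits, which the repeated procedures imply; and raw stair times are not compared with outside values, for which the plan makes no provision. No change to the plan is needed.

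### The satisfaction questionnaire is planned only at Visit 2, so participants who withdraw have no planned way to rate the class, and the primary acceptability mean is likely too high if leavers are less satisfied

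*Combined protocol and SAP*

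**What the plan says.** All places are in the combined protocol and SAP.

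- **Hypothesis (I. Specific Aims, 1c):** "Participants will rate the intervention as acceptable and satisfactory, as measured by a post-intervention survey".
- **Schedule (III. Methods, Protocol, Post-Intervention Visit Two):** the visit follows the programme: "All assessments and procedures will be repeated after completion of the barre exercise program". The satisfaction survey is then added: "An additional survey will be administered, measuring participant experiences with the exercise classes, including satisfaction and acceptability". The survey is not named there. The CSQ is the only satisfaction instrument in the plan, so I take them to be the same.
- **Outcome (III. Methods, Outcome Measures, Primary Outcomes):** the CSQ is summarised as the "mean group rating on measure of self-reported satisfaction of a program".
- **Criterion (IV. Statistical Analyses, Aim 1):** acceptability requires an average above 1.5 out of 4.
- **Tolerated dropout (same section):** "75% of recruited participants will complete the intervention and remain enrolled for the duration of the study".

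The plan describes no exit survey, early-termination visit, record of reasons for withdrawal, analysis population for the CSQ or rule for missing ratings. The one rating taken during the programme is a difficulty scale after each class, used to set progression. It does not measure satisfaction.

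**The concern.** For most outcomes a missing final visit is a nuisance. For satisfaction it is a more direct problem, because the decision to leave may depend on the thing being measured. The protocol's own Background makes that link: it describes conventional exercise programmes as sometimes unenjoyable and prone to attrition, and it expects barre to raise enjoyment and adherence together. If enjoyment helps keep people in the study, those who leave will tend to be those who liked the class less, and the schedule has no planned way to hear from them.

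At stake is the acceptability estimate, which is one of the main products of this pilot. A mean described as the group's would be the mean of those who stayed. In a sample of 15 each missing person is about 7% of the total (1/15).

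**Working it through.** The plan gives no calculation on this point, so there is no figure of its own to reproduce.

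**Inputs from the plan.** N = 15 (I. Specific Aims: "Individuals with PD (N=15) will be recruited to participate in a pilot barre exercise class led by a certified barre instructor"); retention target 75%; acceptability cut-off c = 1.5 out of 4.

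**Assumptions.** The ratings are illustrative. The plan does not state the lowest possible rating, so floors of f = 1 and f = 0 are both shown. All leavers are taken to have attended at least one class; anyone leaving before that has nothing to rate.

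**1. How many can be unrated with retention met.** 0.75 x 15 = 11.25, so 12 must remain (12/15 = 80%). A fourth loss gives 11/15 = 73.3%, which fails. Hence k = 3 at most.

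**2. Bias in the reported mean.** Bias = (k/N) x (completers' mean - leavers' mean). With k = 3 this is 3/15 = 0.2 times the gap.

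| Assumed gap | Bias |
|---|---|
| 0 | 0 |
| 0.5 | 0.10 |
| 1.0 | 0.20 |
| 2.0 | 0.40 |

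Example: completers at 3.0 and leavers at 1.0 give a reported mean of 3.0, while the mean of all 15 is (12 x 3.0 + 3 x 1.0)/15 = 2.6.

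**3. When the decision changes.** With all leavers at the floor, the completers' mean at which the all-starter mean equals the cut-off is (N x c - k x f)/(N - k).

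- k = 3, f = 1: (22.5 - 3)/12 = 1.625
- k = 3, f = 0: 22.5/12 = 1.875

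A completers' mean above 1.5 and up to these values passes although the all-starter mean does not exceed 1.5. For example, 1.6 becomes (12 x 1.6 + 3 x 1)/15 = 1.48, or 19.2/15 = 1.28 with a floor of 0. With 5 leavers the limits would be (22.5 - 5)/10 = 1.75 and 22.5/10 = 2.25, but retention would then have failed at 10/15.

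**4. How likely the situation is.** If each participant stays independently with an assumed probability of 0.75 to 0.90, the chance of at least one withdrawal is 1 - 0.75^15 = 0.987 to 1 - 0.90^15 = 0.794.

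**The case against.** Several points on the other side stand.

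- **The direction is not certain.** A reader might infer that the mean is necessarily inflated. The plan has no data on why people leave, and its Background lists barriers such as lack of time that need not reflect dislike of the class. If nobody withdraws, or withdrawal is unrelated to satisfaction, the bias is zero.
- **Poor attenders are not lost.** A reader might infer that everyone who disliked the class goes unheard. The Outcome Measures section counts participants as retained whatever their attendance, and payment for Visit 2 is not made conditional on attendance. Someone who stops coming but stays enrolled can still rate. The plan is also silent on whether those who withdraw are invited to Visit 2, so the text supports no planned route, not a definite exclusion.
- **Departures are visible.** A reader might infer that the trial could lose its unhappy participants and still look successful. Retention is itself a primary outcome with all recruited participants in the denominator, and early leavers will usually miss the attendance target too. More than 3 losses fails retention outright. But retention shows how many left, not what they thought of the class.
- **The decision is rarely affected.** In the 3.0 versus 2.6 example both values pass.
- **A pooled mean changes what is measured.** Someone who attended one class and someone who attended 24 rate different exposures. This is a fair reason not to make the all-starter mean the sole criterion, though not a reason to leave leavers unasked.

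**Conclusion.** The concern holds in a limited form. As written, the primary acceptability mean comes from those who reach Visit 2. Participants who withdraw, up to 3 of 15 with retention still met, have no planned route to rate the class. The mean is likely biased upward if leavers are less satisfied, an assumption that the protocol's own reasoning about enjoyment and adherence makes plausible but does not prove.

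The effect falls mainly on the reported mean, by a few tenths of a point under the assumed gaps. A changed decision needs a completers' mean just above the cut-off and leavers at or near the scale floor, which is a worst case. The plan should be changed because the remedy is cheap and acceptability is a primary objective, but this does not invalidate the trial.

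**What to change.** In the Post-Intervention Visit Two section, state that the CSQ is also offered by phone, mail or online link, at the time of stopping, to anyone who attended at least one class and withdraws from the study.

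In Statistical Analyses, Aim 1, state that the report will give:

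- the number of raters out of all who started;
- completers' and leavers' means separately;
- the all-starter mean against the 1.5 threshold, alongside the completers' mean;
- a sensitivity analysis that places non-responding leavers at the scale floor, with the floor stated.

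If classes have already finished, the count of raters and the sensitivity analysis can still be added.

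**Cost.** One short questionnaire for a handful of people, with no laboratory visit or sensors. Consent wording must allow the contact. Some leavers may decline, the mean may be slightly lower, and leavers will be rating a shorter exposure to the programme, which is why the two groups should be shown separately.

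### The primary acceptability cut-off, a mean CSQ above 1.5 out of 4, lies below the scale midpoint, so a class that most participants rate in the lower half can be declared acceptable

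*Combined protocol and SAP*

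**What the plan says.** Four places in the combined protocol and SAP bear on this point.

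- Section I, Hypothesis 1c states the claim without a number: "Participants will rate the intervention as acceptable and satisfactory, as measured by a post-intervention survey".
- Section III, Post-Intervention Visit Two provides for the data: "An additional survey will be administered, measuring participant experiences with the exercise classes, including satisfaction and acceptability".
- Section III, Outcome Measures lists the CSQ among the three primary outcomes, summarised as "mean group rating on measure of self-reported satisfaction of a program".
- Section IV, Aim 1 supplies the only decision rule. Acceptability is "defined as a minimum average rating of > 1.5 out of 4 on the Client Satisfaction and Acceptability Questionnaire (CSQ".

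The other two primary criteria, in the same Section IV list, are "75% of participants will attend 75% of the 24 sessions" and "75% of recruited participants will complete the intervention and remain enrolled for the duration of the study".

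Nowhere does the plan give the CSQ's lowest score, its direction, its response labels, its number of items, or a source or reason for 1.5. It also sets no second acceptability condition, such as a minimum share of satisfied participants. By contrast, the improvement thresholds for the Mini-BESTest, Five Times Sit to Stand, forward gait speed and PDQ-39 each carry a reference.

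**The concern.** A threshold for calling a programme acceptable should lie in the favourable half of the scale. On the two natural readings of a scale with maximum 4, the value 1.5 lies in the unfavourable half. Hypothesis 1c could then be declared supported when most respondents, or on a 1-4 scale all of them, rated the class below the midpoint.

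This matters more here than in most pilots. Feasibility and acceptability are the primary outcomes, and the motor results are to be reported only as trends. A favourable acceptability statement is one of the three main conclusions the study can reach, and the present rule does little to protect it.

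**Working it through.** **Inputs from the plan.** Cut-off: mean above 1.5, stated maximum 4 (Section IV, Aim 1). Sample size 15: "Individuals with PD (N=15) will be recruited to participate in a pilot barre exercise class" (Section I). Retention target 75%: 0.75 × 15 = 11.25, so at least 12 completers. The plan gives no derivation of 1.5, so there is no figure to reproduce.

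**Assumptions.** Higher means more satisfied, as a minimum rating combined with a greater-than sign implies. The floor is 0 or 1. For the counts only, each person gives one whole-number rating.

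**Step 1: position of the cut-off.** Midpoint = (min + max)/2; position = (1.5 − min)/(max − min).

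- 1-4: midpoint (1 + 4)/2 = 2.5; position 0.5/3 = 16.7% of the way up.
- 0-4: midpoint (0 + 4)/2 = 2.0; position 1.5/4 = 37.5% of the way up.

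**Step 2: groups that pass or fail, n = 15.** The rating sum must exceed 15 × 1.5 = 22.5.

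- 1-4, seven 1s and eight 2s: 23/15 = 1.53, passes with nobody above the midpoint.
- 1-4, eight 1s and seven 2s: 22/15 = 1.47, fails. So not every such group passes.
- 1-4, k people in {1, 2} and the rest in {3, 4}: the smallest sum is k + 3(15 − k) = 45 − 2k. This exceeds 22.5 for k up to 11, so every group with 8 to 11 of 15 in the lower half passes. The lowest case is eleven 1s and four 3s: 23/15 = 1.53.
- 0-4, nine 0s and six 4s: 24/15 = 1.60, passes.
- 0-4, twelve 1s and three 4s: 24/15 = 1.60, passes. Thirteen 1s and two 4s give 21/15 = 1.40 and fail, so 12 is the most that can be below the midpoint.

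**Step 3: how many lower-half-majority patterns pass.** A pattern is the number of respondents in each category. All patterns with more than half of respondents below the midpoint were enumerated.

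| Scale, n | Patterns | Pass at > 1.5 | Pass at > midpoint |
|---|---|---|---|
| 1-4, 15 | 408 | 377 (92%) | 50 (12%) |
| 0-4, 15 | 1,290 | 461 (36%) | 41 (3%) |
| 1-4, 12 | 203 | 180 (89%) | 13 (6%) |
| 0-4, 12 | 518 | 124 (24%) | 7 (1%) |

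The first row can be checked by hand. With k in the lower half there are (k + 1)(16 − k) patterns, and k = 8 to 15 gives 72 + 70 + 66 + 60 + 52 + 42 + 30 + 16 = 408. Patterns with sum 22 or less occur only for k = 12, 13, 14 and 15 and number 3 + 9 + 11 + 8 = 31, leaving 408 − 31 = 377. These are counts of what the rule permits, not probabilities.

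**Step 4: other codings.**

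- If 1 were the best answer, the inequality would point the wrong way: all-best ratings (mean 1.0) fail and all-worst ratings (mean 4.0) pass.
- A 0-3 coding would put 1.5 exactly at the midpoint, (0 + 3)/2, but does not fit a scale described as out of 4.

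**The case against.** The strongest reply is that the instrument is undefined, so the fault may lie in its description and not in the number. Four response options coded 0-3 could loosely be called out of 4, and a mean above 1.5 would then already be above the midpoint. The documents cannot rule this out. It is a good reason to define the scale before changing the number, but it does not defend the text as written, because the literal reading has a maximum of 4.

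Other points stand in part:

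- Without response labels, the midpoint is only a proxy for the line between satisfied and dissatisfied. The finding is about ratings below the numeric midpoint.
- The two scales are not equally affected. On 0-4, a passing group with a majority below 2 needs some 3s or 4s; if the rest all rate exactly 2, at most 7 of 15 can be below.
- Any rule based on a mean admits some such groups. Even at the midpoint, up to 11 of 15 could be below on 1-4 (eleven 2s and four 4s: 38/15 = 2.53), or 9 of 15 on 0-4 (nine 1s and six 4s: 33/15 = 2.20). But a midpoint rule cannot pass a group that is entirely below the midpoint; on 1-4 the present rule can.
- If the CSQ is scored as an average over several items, the counts in Step 3 do not carry over. The midpoint comparison in Step 1 does.
- The 75% criteria are proportions of people and this one is a mean, so the contrast shows leniency and is not a contradiction.

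It can also be said that this is a pilot of 15, that the mean will be reported whatever label it gets, and that no go/no-go decision is tied to it. That limits the harm. The label is nevertheless a stated primary conclusion.

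**Conclusion.** The concern holds. As written, the rule deciding Hypothesis 1c sits 16.7% of the way up a 1-4 scale or 37.5% of the way up a 0-4 scale. On 1-4, all 15 participants can rate the class 2 (mean 2.0) and it is declared acceptable; on 0-4, up to 12 of 15 can be below the midpoint. The conclusion that 1.5 is too low rests on higher scores being better and on a maximum of 4. The numbers of people and the pattern counts rest also on one whole-number rating each. Reverse coding would leave a different error, in the direction of the inequality. Only a 0-3 coding would place the cut-off at the midpoint, and the scale description would then need correcting. Because a primary conclusion can be wrong under the stated rule, this must be corrected.

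**What to change.** 1. State the CSQ's range, direction, number of items and how the group mean is formed.
2. Replace the cut-off with a justified value in the satisfied half of the scale, at minimum above the midpoint: above 2.5 if scored 1-4, above 2.0 if scored 0-4. A mean of at least 3 is one stricter option. With whole-number ratings and 8 of 15 below the midpoint, the highest possible mean is (8×2 + 7×4)/15 = 2.93 on 1-4 or (8×1 + 7×4)/15 = 2.40 on 0-4, so no such group could pass. With item averages this guarantee weakens on 1-4, because the bound approaches (8×2.5 + 7×4)/15 = 3.20.
3. If 1 proves to be the best score, reverse-score the items or reverse the inequality.
4. Report the distribution of ratings and the number of respondents beside the mean, since a midpoint rule still passes some groups with a majority below it.
5. If CSQ data have already been seen, report the present criterion as pre-specified and label the revised one post hoc. The documents do not state recruitment status.

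The cost is one line for the criterion and one for the scale definition, with no new data collection. The downside is that the criterion becomes harder to meet.
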